9.4 Reporting of Events

For all adverse events, all sections of the appropriate Case Report Form (CRF) must be completed.

- All AEs, SAEs, SADEs, and/or UADEs/USADEs must be reported on the appropriate eCRF.
- Any device related AEs, must be reported to the Sponsor within one (1) working day of the site/investigator becoming aware of the event.
 - De-identified copies of all relevant documentation (i.e., procedure reports, physician / nurses' notes, discharge summary, etc.) should be submitted to the Sponsor within 72 hours of knowledge of a UADE or death, as appropriate.
 - UADEs / USADEs will be evaluated and assessed / escalated by the Sponsor per ISO 14155:2020 and as per local regulations.

Table 4: Reports and Notifications Required from Clinical Investigators

Safety Event Type	Notification to:	Reporting Timeline
Device/procedure related AEs / SAEs, ADEs / SADEs, or UADEs / USADEs	Sponsor and IRB (if applicable)	No > than 1 business day of becoming aware of event
Death(s) (All-Cause)	Sponsor and IRB (if applicable)	No > than 1 business day of becoming aware of event
Device Deficiencies	Sponsor and IRB (if applicable)	As soon as possible, but no later than one (1) working day after site awareness and per local IRB / EC requirements. The device(s) should be returned to Sponsor. Any device deficiency that did not lead to an AE but could have led to a SADE, if suitable action had not been taken, if intervention had not been made or if circumstances had been less fortunate must be reported to the Sponsor within one (1) working day of the event.
Requests for or Reports of Significant Deviations	Sponsor and IRB (if applicable)	As soon as possible, but no later than five (5) working days after emergency / deviation occurs
Failure to Obtain ICF	Sponsor and IRB (if applicable)	Within five (5) working days after index procedure.
Withdrawal of IRB	Sponsor and IRB (if applicable)	Immediately by telephone followed by a copy of the notification within five (5) working days.
Investigation Suspension / Premature Termination	IRB	The PI must notify the IRB of all terminations / suspensions. The PI must notify the IRB in writing as soon as possible but no later than within ten (10) working days (or sooner as required by the IRB) if the premature termination is related to safety or compliance issues.

Notice of Inspection or Audit by the Health Authorities	Sponsor	As soon as possible after becoming aware of the impending inspection / audit.
---	---------	---

It is the responsibility of the Investigator to report adverse events to individual Institutional Review Boards (IRBs) according to the local governing IRB's requirements.

9.5 Safety Committees

9.5.1 Medical Monitor

The Medical Monitor (MM) will be responsible for AE trending review as well as for the identification of signals that could indicate a serious health threat as specified in the Safety Management Plan.

10 STATISTICAL METHODS

10.1 Overview of Study Design

This is a prospective, multi-center, single-arm study designed to assess the safety and performance of the Pristine™ Long-Term Hemodialysis Catheter for Attaining Vascular Access for Hemodialysis by comparison to a performance goal derived from the Dialysis Outcomes and Practice Patterns Study data.

10.2 Sample Size Considerations

The primary objective of the study is to show the overall complication rate for Pristine is non-inferior to the performance goal at 3 months. If successful, the next step is to show superiority of Pristine at 3 months.

Based on hypothesis test of Non-inferiority

- Assumptions:
 - The complication rate of our performance goal is estimated at 31.5 events per 1000 patient days with a 90 days follow-up based on DOPPS study data. The complication rate for Pristine is expected to be similar.
 - The performance goal is set at 36.5 events per 1000 days using a 5 events per 1000 days non-inferiority margin;
 - The attrition through 90 days is assumed to be 15%
 - The Type 1 error is 0.025 (one-sided).

- The Type 2 error is 0.2.
- Sample Size:
 - Total required exposure is 12765 patient days which translates to 142 participants with average exposure of 90 days (PASS 2019).

Based on hypothesis test of Superiority

- Assumptions:
 - The complication rate of our performance goal is estimated at 31.5 events per 1000 patient days with a 90 days follow-up based on literature review, which is set as the performance goal.
 - The complication rate for the Pristine™ Catheter is assumed to be 26.5 events per 1000 patient days.
 - The attrition through 90 days is assumed to be 15%
 - The Type 1 error is 0.025 (one-sided).
- Sample Size:
 - Total exposure of 12765 patient days (which translates to 142 participants with average exposure of 90 days) will provide 85% power of the test (PASS 2019).

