Despite the burden of catheter-associated conditions and risks for patients, the use of cuffed tunneled central venous catheters is frequently vital as a standalone treatment modality of acute and chronic renal failure and serves as a bridge until recovery of renal function, maturation of fistula, or finding a donor organ. The need for better performing hemodialysis catheters still exists.

Catheter design can impact performance. Some hemodialysis catheters have side holes in their distal lumens. These side holes, which were intended to increase inflow and reduce risk of blockage, have been shown to be prone to clot formation. Under electron microscopy side holes have been shown to have rough edges where thrombi can attach. Due to the side holes flow, anticoagulant given at the end of dialysis may not be able to reach the tip of the catheter.

The Pristine™ Long-Term Hemodialysis Catheter, is an innovative split, symmetrical, side-hole-free tip. The Pristine™ Catheter's side-hole free tip is designed to help minimize thrombus adhesion that can be associated with hemodialysis catheters that have side holes.

In a previous feasibility study, the primary objective was to observe the performance of the Pristine™ Long-Term Hemodialysis Catheter in participants with End-Stage Renal Disease or Acute Renal Failure. The study was performed at a single investigation site in the Dominican Republic. Forty-five (45) participants (males or non-pregnant females with ESRD or ARF requiring hemodialysis treatment) received the current 15.5F Pristine™ catheter. The primary endpoint was primary patency, prespecified for evaluation at 30 days post-catheter implantation and was defined as a catheter that provided adequate hemodialysis (flow >300mL/min) without the need for additional interventions (i.e., TPA infusions or fibrin sheath stripping or catheter exchange) to maintain flow or correct device failure.³

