Participants were followed for 6 months post-catheter implantation at four sites that were affiliated with the placement institution. All catheters (n=44) were patent at 30 days post implantation. Primary patency at 60- and 180- days post procedure was 100.0% and 90.9%, respectively. The following adverse events (AE) were reported in accordance with MedDRA v. 22.1. There were 9 infections, 6 of which were reported as device-related and 3 (2 pneumonia and 1 abdominal abscess) were reported as not related to the study device. There were 2 cardiac disorders and 2 vascular disorders, none of which were reported as device related. There were 6 general disorder and access site conditions, 2 of which were reported as device related. There were 9 deaths reported in the study, none of which were reported as related to the device or procedure.³

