3 OBJECTIVES AND ENDPOINT

The objective of this study is to assess the safety and performance of the BD Pristine™ Long-Term Hemodialysis Catheter for attaining vascular access for hemodialysis. The information obtained from the study is intended to be reported in the device's labeling.

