4.2 Scientific Rationale for Study Design

The combined safety and performance primary endpoint is compared to a performance goal of 31.5 complications per 1000 catheter days derived from the Dialysis Outcomes and Practice Patterns Study (DOPPS).⁵ The DOPPS data was chosen due to it's significant sample size of tunneled catheters (n=4207) and it's clear definition of non-infectious and infectious complications. DOPPS I-III enrolled 27, 129 participants that provided access data. DOPPS I enrolled within France, Germany, Italy, Japan, Spain, the United Kingdom, and the United States. DOPPS II and DOPPS III enrolled in Australia, Belgium, Canada, New Zealand, and Sweden.⁵ There have been few hemodialysis catheter studies performed in the last 10 years with many lacking sufficient sample size for statistically powered endpoints. The hemodialysis catheter studies that report 'complication' rates or infection rates have a significant variance in definitions. The KDOQI guidelines have stated a need for consistent definitions and outcomes between tunneled catheter studies.⁶ DOPPS is a globally renowned study providing clinically meaningful definitions with a significant sample size not seen in other studies.

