The primary endpoint for this study is a combined complication rate of non-infectious and infectious complications. Non-infectious complications are defined as, complications due to any noninfectious cause (thrombosis of the access, fibrin material within or around a catheter, catheter migration, central vein stenosis or thrombosis) requiring a revision procedure to maintain patency or improve access performance (i.e., thrombolysis, angioplasty, or surgical correction) in an inpatient or outpatient setting or removal or abandonment with creation of a new access that was not due to an access-related infection). This definition of non-infectious provides the clinically relevant point of re-intervention. Thrombosis, fibrin material, and catheter migration are all common events for tunneled catheters. When these events start to disrupt dialysis treatment, they require re-intervention thus putting more burden on the patient and healthcare system. The other part is infectious complications defined as, complications due to any documented diagnosis of access infection requiring medical intervention (managed in an outpatient or inpatient setting) or sepsis as diagnosis in the hospitalization file whether access related or not. Infection rate for catheters is arguably the most crucial reported value being the main cause of catheter related deaths. The infectious complications defined include exit site infections and all blood stream infections causing sepsis.

Showing a statistically significant difference by our powered primary endpoint against the performance goal will attest to the performance, safety, and clinical benefits of the Pristine™ Catheter.

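### SAP 5.2.2 sets the superiority goal at 26.5 per 1000 patient-days, against 31.5 in SAP 2.4 and Protocol 10.5; as written, the test has about 2.4% power at the planned rate, not 85%

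*Protocol*

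**What the plan says.** Protocol 10.5 and SAP 5.2.2 specify two sequential one-sided tests of a Poisson rate at 0.025. The first compares Pristine with 36.5 per 1000 patient-days, which is the DOPPS-based 31.5 plus a margin of 5. The second, run only if the first succeeds, tests superiority.

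The superiority goal appears in four places:

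- Protocol 1.1 (synopsis, statistical methods): 31.5
- Protocol 10.5: 31.5
- SAP 2.4 (superiority sample size): 31.5, with an assumed Pristine rate of 26.5 and 85% power
- SAP 5.2.2 (hypothesis testing): 26.5

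Protocol 10.2 carries the same superiority inputs as SAP 2.4. For the non-inferiority calculation it says of the benchmark rate: "The complication rate for Pristine is expected to be similar". Protocol 4.2 describes the benchmark this way: "The combined safety and performance primary endpoint is compared to a performance goal of 31.5 complications per 1000 catheter days". The SAP revision history lists only the original version, so no recorded change accounts for 26.5.

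**The concern.** SAP 5.2.2 is the section an analyst will program from. There the goal equals the rate at which the device is planned to perform. A test of whether the rate lies below 26.5, when it is in fact 26.5, can succeed only by type I error, yet the same SAP claims 85% power.

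With two goals on file for one confirmatory test, a wide band of results would be superior under the protocol and not superior under SAP 5.2.2. If the conflict is settled after the counts are known, the choice of goal decides the claim. That matters because Protocol 4.2 says a significant result "will attest to the performance, safety, and clinical benefits" of the catheter, and Protocol 3 intends the findings for the device labelling.

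**Working it through.** **Inputs.** Goals 36.5, 31.5 and 26.5; assumed true rates 31.5 (non-inferiority) and 26.5 (superiority); one-sided alpha 0.025; attrition 15%; total exposure 12,765 patient-days, 142 participants (Protocol 10.2, SAP 2.4).

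**Method.** For goal λ0 and exposure T in days, the critical count c is the largest integer with P(X ≤ c) < 0.025 when X is Poisson with mean λ0·T/1000. Power at true rate λ is P(X ≤ c) with mean λ·T/1000.

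**Reproducing the plan's figures.** 12,765 × 0.85 = 10,850 days, and 12,765 / 90 = 141.8, giving 142 participants. At 10,850 days:

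- Non-inferiority, goal 36.5: c = 357; power at 31.5 is 80.3% (plan: 80%).
- Superiority, goal 31.5: c = 305; power at 26.5 is 85.5% (plan: 85%).

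Both stated powers reproduce if 12,765 is the exposure inflated for attrition. The documents do not say this outright, so results at the full 12,765 days are shown as well.

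**Superiority at a true rate of 26.5**

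| Goal | Exposure (days) | Critical count | Power |
|---|---|---|---|
| 31.5 | 10,850 | 305 | 85.5% |
| 31.5 | 12,765 | 362 | 90.5% |
| 26.5 (SAP 5.2.2) | 10,850 | 254 | 2.4% |
| 26.5 (SAP 5.2.2) | 12,765 | 302 | 2.4% |

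SAP 5.2.2 also mentions a chi-square p-value from a Poisson regression. A normal approximation at 10,850 days gives 85.6% and 2.5%, so the choice of test does not drive the result.

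**True rate needed for 85% power against 26.5:** 22.0 per 1000 at 10,850 days, 22.3 at 12,765 days.

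**Where the two documents disagree.** At 10,850 days, any count from 255 to 305 (255/10,850 = 23.5 to 305/10,850 = 28.1 per 1000) is superior under Protocol 10.5 and not under SAP 5.2.2. At a true 26.5 the chance of landing there is 85.5% − 2.4% = 83.1%.

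**Supporting note on 31.5.** Over 90 days, 31.5 × 0.09 = 2.84 and 36.5 × 0.09 = 3.29 complications per patient. Protocol 4.2 names DOPPS and 4207 tunneled catheters but gives no event count, person-time or calculation.

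The feasibility study in Protocol 2.1 used patency "without the need for additional interventions (i.e., TPA infusions or fibrin sheath stripping or catheter exchange") as its endpoint and reports: "All catheters (n=44) were patent at 30 days post implantation"; "Primary patency at 60- and 180- days post procedure was 100.0% and 90.9%, respectively"; "There were 9 infections, 6 of which were reported as device-related". If 90.9% refers to all 44 catheters, about 4 lost patency. The exposures below are assumptions, since person-days are not given.

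| Events counted | 44 × 180 = 7,920 days | 44 × 60 = 2,640 days | 44 × 30 = 1,320 days |
|---|---|---|---|
| 9 infections + 4 losses = 13 | 1.6 | 4.9 | 9.8 |
| All 19 listed adverse events + 4 losses = 23 | 2.9 | 8.7 | 17.4 |

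These rates per 1000 days run from about 2 to 17, all below 26.5.

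**The case against.** The discrepancy does not favour the device. A goal of 26.5 is stricter than 31.5, and the acceptance criterion in SAP 2.8 uses only 36.5, so no false success follows and the non-inferiority conclusion is unaffected. That stands. What remains is a superiority test that would very probably fail at the planned rate and a prespecified goal that is ambiguous.

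It could also be said that 26.5 was meant as superiority by a margin, since 31.5 − 5 = 26.5. SAP 5.2.2 states no such margin and gives 31.5 as the control rate in its own opening paragraph. SAP 2.4 makes 31.5 the superiority goal. Even on that reading the 85% power would not apply.

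A reader might go further and infer that the benchmark of 31.5 is wrong, or that the feasibility data contradict the planning sentence. The documents do not support either. Setting the true rate equal to the benchmark is an ordinary sizing assumption for non-inferiority; it enters no decision rule, and a lower true rate only raises power. The feasibility study had one placement site outside the US, included acute renal failure, measured patency status rather than complication counts, and gave no person-days or repeat revisions. The missing arithmetic may be in the cited source. Nor does a pass stand alone as evidence: SAP 5.2.2 reports the estimated rate with a 95% confidence interval.

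**Conclusion.** The superiority goal in SAP 5.2.2 is inconsistent with Protocol 1.1, Protocol 10.5 and SAP 2.4, and the SAP's 85% power statement does not describe the test it specifies. At the planned rate of 26.5 the power is 2.4% instead of 85.5%, under either reading of the exposure for the lower figure. The calculation assumes a constant-rate Poisson count, as the plan does, and 10,850 or 12,765 patient-days. The sample-size arithmetic itself is sound on its stated inputs.

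The note on the benchmark is a request for verification. The rates of 31.5 and 36.5 are hard to reconcile with the Pristine data in Protocol 2.1, but that comparison rests on assumed exposure, an inferred number of patency losses, and a different endpoint and population. It does not establish an error.

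**What to change.** Before the 3-month analysis, change 26.5 to 31.5 in the superiority sentence of SAP 5.2.2 so that it matches Protocol 10.5 and SAP 2.4, and record the change and its date in the SAP revision history. This costs one figure and one log entry. It adds no patients, visits or data.

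At the same time, check 31.5 and its unit against the cited DOPPS publication and put the events, person-time and calculation on file. If the figure is confirmed, nothing else in the design changes. If it is not, the goals and power statements that depend on it would need revisiting; the size of that effect cannot be stated from these documents.

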10.3 Analysis Population

Sites will be limited to enrolling 20% (28) of the total sample size. The following populations are defined:

Table 5: Analysis Population List

Population	Description
Enrolled	All participants who sign the ICF will be classified as enrolled.
Intent-to-Treat (ITT)	The intent-to-treat population will consist of all participants into whom has signed the ICF, met all inclusion/exclusion criteria, and the Pristine™ Catheter was placed.
Per-Protocol	A Per-Protocol (PP) population may be created if there are participants who have any major deviations. The PP population will consist of any participants in the ITT population who do not have any major deviations. The deviations that are considered to have a “major” grade will be defined a priori in the SAP.

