5.4 Screen Failures

Individuals that consent to participate in the study but subsequently fail to meet eligibility criteria and do not undergo treatment with the study device at the Index Procedure will be considered SCREEN FAILURES. Study participation for screen failures will end at the time of

eligibility failure and these individuals may not be rescreened. Documentation of the reason(s) for screen failure should be present in the participant's medical record and/or source documents.

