7.4 Participant Follow-Up

7.4.1 Follow-Up Intervals and Methods

Enrolled participants will have follow-up visits at 1-month, 3 months, 6-months, and 12-months via either in person visit or telephone call. For participants into whom the Pristine™ Catheter was introduced during the index procedure, but procedure success was not achieved, only the procedure eCRF will be collected and limited to the collection of safety events and interventions for up to 30 days.

Follow-up windows will be calculated from the index procedure date. Refer to Section 1.2 for an overview of follow-up window time frames and requirements for each visit. The

following data will be collected and documented on the appropriate eCRF for each follow-up unless otherwise specified for treated participants:

- Hemodialysis Catheter Assessment:
 - Document how the participant has been receiving hemodialysis and document the date of the participant's last HD session.
- Dialysis Session Blood Flow Rate:
 - If dialyzing through the Pristine™ Catheter, document the reported dialysis sessions and details such as date of dialysis session, average blood flow rate, number of line reversals, and length of dialysis session.
- If Needed:
 - Documentation of any protocol deviations that have occurred since the last follow-up.
 - Documentation of occurrence and / or status of AEs since the last follow up (refer to Section 9).
 - Any catheter reinterventions the participant has undergone since the prior follow-up.

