Serious Health Threat	Signal from any AE or device deficiency that indicates an imminent risk of death or a serious deterioration in the health in participants, users, or other persons, and that requires prompt remedial action for other participants, users, or other persons. This would include events that are of significant and unexpected nature such that they become alarming as a potential serious health hazard or possibility of multiple deaths occurring at short intervals.
Severe AE	Symptom(s) causing severe discomfort to the participant and / or significant impact on the participant's usual activity. Additional intervention and / or treatment is necessary. Additional sequelae occur.
Severity (of AE)	The intensity of the AE as experienced by the participant or user.
Significant Deviation	A deviation that occurs to protect the life or physical well-being of a participant in an emergency, or a deviation that may affect the

Term	Definition
	scientific soundness of the clinical investigation, or a deviation pertaining to the rights, safety or welfare of human participants.
Source Data	All information in original records, certified copies of original records of clinical findings, observations, or other activities in a clinical investigation, necessary for the reconstruction and evaluation of the clinical investigation. This includes electronic source data initially recorded in an electronic format.
Source Document	Original or certified copy of printed, optical, or electronic document containing source data.
Sub-Investigator	Individual member of the investigation site team designated and supervised by the PI at an investigation site to perform clinical investigation-related procedures or to make important clinical investigation-related and medical treatment decisions.
Thrombosis	The formation or presence of a blood clot resulting in catheter occlusion.
Treated Participant	Defined as a participant that has met all eligibility criteria, into whom the Pristine™ Long-Term Hemodialysis Catheter was introduced and in whom procedure success was achieved.

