## 4 Analysis Population Set(s)

### 4.1 Population Definitions

The following populations are defined:

Table 2: Analysis Population List

Population	Description
Enrolled	All participants who sign the ICF will be classified as enrolled.
Intent-to-Treat (ITT)	
The ITT population will consist of all participants who have signed the ICF, met all inclusion/exclusion criteria, and had the procedure initiated.
 
The ITT population includes the following three groups on the Subject Disposition CRF page: Eligibility met but device not inserted, Device inserted but subject did not undergo first dialysis session, and Treated with study device.

Modified Intent-to-Treat (mITT)	
The mITT population will consist of all ITT participants treated with the study device.
 
The mITT population includes subject treated with study device on the Subject Disposition CRF page.

Per-Protocol (PP)	
A PP population may be created if there are participants who have any major deviations. The PP population will consist of any participants in the mITT population who do not have any major deviations. The deviations that are considered to have a “major” grade will be identified and summarized in Appendix 3 prior to data analyses.

All endpoints will be analyzed primarily based on the mITT population and ITT population where applicable. PP analyses may also be performed for the primary endpoints and will only serve as sensitivity analyses.

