# **7 Safety Analysis**

Collection of AEs will begin immediately following subject enrollment, during the index procedure through final subject follow-up visit or early termination.

An overall summary including the number and percentage of subjects with at least one AE, total number of AEs, total number of SAEs, total number of UADEs, AEs by relationship to the Device/Index Procedure, and AEs by severity of the event will be summarized for the ITT subjects. In addition, the following summary tables will be provided:

- Number of AEs by System Organ Class (SOC) and Preferred Terms (PT)
- Number of SAEs by System Organ Class (SOC) and Preferred Terms (PT)
- Number of AEs by relationship to Study Device by System Organ Class (SOC) and Preferred Terms (PT)
- Number of AEs by relationship to Procedure by System Organ Class (SOC) and Preferred Terms (PT)
- Number of AEs by severity by System Organ Class (SOC) and Preferred Terms (PT)

Listing of all AEs, SAEs, ADE, and UADEs will be provided.

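### ITT membership requires that all eligibility criteria were met, so a catheter recipient later found ineligible leaves the primary set on the literal text but stays in under the SAP's CRF mapping

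*Protocol*

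**What the plan says.** Protocol 10.3, Table 5, defines ITT as "all participants into whom has signed the ICF, met all inclusion/exclusion criteria, and the Pristine™ Catheter was placed". SAP 4.1, Table 2, defines it as those who have "signed the ICF, met all inclusion/exclusion criteria, and had the procedure initiated". The two differ on the last condition (placed against initiated), but both require eligibility.

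In SAP Table 2, mITT is the part of ITT treated with the device, and PP is the part of mITT without major deviations. The SAP runs the primary test on mITT with PP as sensitivity analysis (5.2.1, 5.2.2). Protocol 10.5 runs it on ITT with PP as sensitivity analysis.

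SAP Table 2 also describes ITT and mITT by categories on the Subject Disposition CRF page. One of these is *Treated with study device*, and it carries no eligibility label.

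Related definitions:
- Protocol 5.4: those who "fail to meet eligibility criteria and do not undergo treatment with the study device at the Index Procedure will be considered SCREEN FAILURES". A person who received the device is therefore not a screen failure.
- Protocol Appendix A, Treated Participant: "Defined as a participant that has met all eligibility criteria, into whom the Pristine™ Long-Term Hemodialysis Catheter was introduced", with procedure success as a further condition.
- Protocol 7.4.1 lists follow-up eCRF data "unless otherwise specified for treated participants".
- SAP 7: the overall AE overview "will be summarized for the ITT subjects".

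**The concern.** Eligibility can be re-judged after the catheter is in. A record of infection in the week before enrollment may surface later, or a central venous stenosis may prove to have been known already. Such a breach would usually be handled as a protocol deviation that affects the per-protocol set. Here, on the literal wording, it removes the participant from every analysis set that the primary endpoint uses.

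The trial has one arm and no blinding (SAP 2.3), and Protocol 7.1.5 requires no laboratory tests for study participation. An early complication may therefore be what prompts a second look at the chart. Four exclusions in Protocol 5.2 (active infection, bacteremia or infection within 7 days, known central venous stenosis, uncontrolled coagulation) overlap the endpoint components in Protocol 3.1 (infection, thrombosis, central vein stenosis). If exclusion tends to follow events, the comparison with the performance goal is affected, in a study whose results are intended for labeling (Protocol 3).

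**Working it through.** **1. Where the participant falls.** Take someone who consented, had the catheter placed and used, and was later found to breach a criterion.

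| Rule | Result |
|---|---|
| Screen failure, Protocol 5.4 | No: device was used |
| ITT text, Protocol Table 5 and SAP Table 2 | Out: criteria not all met |
| mITT and PP text, SAP Table 2 | Out: nested in ITT |
| Treated Participant, Protocol Appendix A | Out: eligibility required |
| CRF category, SAP Table 2 | In: treated with study device, no eligibility label |
| Overall AE summary, SAP 7 | Out if ITT is read by its text |
| SOC/PT tables, SAP 7 | No population named |
| AE listing, SAP 7 | In: all AEs, no restriction |
| Stays in follow-up, Protocol 7.5 | In: everyone with the catheter placed |

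The categories in SAP 6.1 attach an eligibility label only to the two groups without an inserted device. There is no category for treated but ineligible.

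**2. The plan's own figures.** Inputs from Protocol 10.2: goal 36.5 and assumed rate 31.5 per 1000 patient days, attrition 15%, "The Type 1 error is 0.025 (one-sided"), "The Type 2 error is 0.2". Exposure after attrition is 12765 × 0.85 = 10850 days. An exact one-sample Poisson test at 10850 days rejects at 357 events or fewer, with power 80.3%. Then 10850/0.85 = 12765, and 12765/90 = 141.8, or 142 participants. Superiority (31.5 against 26.5) at 10850 days has power 85.5%, against 85% stated. The figures reproduce, and this point does not alter them.

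**3. Effect on the rate.** The documents give no count of treated ineligible participants, so the inputs here are assumptions. A share f of those treated is excluded, their complication rate is RR times that of the rest, and exposure per person is equal. Exclusion removes both events and days:

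analysed rate = all-treated rate / ((1 − f) + f × RR)

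| f | RR | Change in rate | 36.5 would read |
|---|---|---|---|
| 5% | 0.5 | +2.6% | 37.4 |
| 5% | 1 | 0 | 36.5 |
| 3% | 1.5 | −1.5% | 36.0 |
| 5% | 2 | −4.8% | 34.8 |
| 10% | 2 | −9.1% | 33.2 |

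For scale, the margin is 5/36.5 = 13.7% of the goal.

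**4. Effect on the test.** Exact Poisson, 142 participants at 90 days each, all-treated rate exactly 36.5, k participants excluded:

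| k | RR | Chance of declaring non-inferiority |
|---|---|---|
| 0 | – | 2.5% |
| 3 | 2 | 6.0% |
| 7 | 0.5 | 0.6% |
| 7 | 1 | 2.5% |
| 7 | 2 | 16.4% |

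At 76.5 days each (90 × 0.85), the RR = 2 results are 5.7% (k = 3) and 13.7% (k = 7).

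**The case against.** The strongest reply is that the SAP's working rule is the CRF category. A catheter recipient found ineligible later would be recorded as treated with the study device and so be in mITT. That may be what happens, but the same table states the eligibility condition in words and does not say which governs. This leaves an ambiguity in the primary analysis set, and the literal reading is not shown to be the one applied.

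A reader might infer that the complication rate is biased downward. The documents do not support that as a fact:
- Direction depends on the excluded participants' rate. Some exclusions (AVF or AVG awaiting maturation, another study) need not raise risk.
- An infection judged to pre-date the device might not count even if the participant stays in. SAP 5.2.1 counts only device-related or likely related events, and Protocol 9.1.1 keeps pre-existing conditions out of AE reporting unless they worsen substantially. Retaining that person could add days without the event.
- Only known stenosis is excluded, and coagulation is judged at enrollment by the physician, so a later finding does not readily reverse either.
- Eligibility is documented before the procedure (Protocol 7.1.6) and waivers are barred (Protocol 7), so numbers should be small.

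A reader might also infer that these participants vanish from safety reporting or follow-up. They do not. Only the overall AE summary names ITT, the listing covers all AEs, and Protocol 7.3 and 7.5 require data collection and continued participation for everyone with the catheter placed. The link through Appendix A to 7.4.1 is weak, because 7.4.1 opens by giving follow-up visits to enrolled participants.

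**Conclusion.** The point holds as a conflict over who is in the primary analysis set. The written definitions exclude a catheter recipient found ineligible afterwards from the primary test, its only sensitivity analysis and the overall AE summary. The SAP's CRF mapping would include the same person. Because the question can be settled after outcomes are known, without blinding or a comparator, it should be closed before analysis.

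Bias is possible and plausibly downward, through the overlap between exclusions and endpoint. Its direction and size are not established. In the assumed cases the rate moves from 2.6% too high to 9.1% too low, with no change at equal rates. Three exclusions of 142 at twice the rate would raise the false-success chance at the goal from 2.5% to 6.0%. Both results rest on the assumed share, rate ratio and equal exposure. The sample size is unaffected.

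**What to change.** 1. Delete the eligibility condition from the ITT definition in Protocol Table 5 and SAP Table 2, and from Treated Participant in Protocol Appendix A. ITT membership then depends on consent and on either procedure initiation or device placement. Choose one of these and use the same wording in both documents. mITT remains those treated with the device.
2. Class eligibility breaches as major deviations in SAP Appendix 3, so that they affect PP only. That appendix is listed but its content is not shown, so confirm whether it already does this.
3. State in SAP 7 that all AE summaries, including the SOC/PT tables, cover at least every participant in whom the catheter was introduced.

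The cost is wording in two tables, one appendix entry and one SAP section. A few ineligible participants stay in the main analysis, and the rate may be slightly less favourable. PP still gives the eligible-only result. The change settles who is counted; it does not alter which events count under the device-relatedness rule.
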